6.2 Placement of the final restoration

Each implant will be restored in the conventional manner with an aesthetically pleasing single crown restoration. Restoring materials will be selected by the restoring dentist based on discretion of the dentist and individual patient needs. Prosthetic restoration of the implants will require numerous visits to the restorative dentist over a period of one to two-months. The restoring dentist will advise when additional visits are necessary. Photographs will document each step in the restoration process and of radiographs be taken of each area when the final restoration is cemented.

7.0 LONGITUDINAL FOLLOW-UP

7.1 Post-Restoration Follow-up Evaluations (12-months and 24-months after implant placement)

Participants will return to the clinic at 12 and 24 months following implant placement. Evaluation of implant function and surrounding tissue health will be determined based on an interview with the participant, clinical examination of the study sites and an analysis of radiographic and photographic data.

At each visit, study personnel will review and update the participant's health history and record any adverse experiences; a study dentist will complete a thorough periodontal evaluation of the implant area and provide an assessment of the prosthetic attachment interface. A set of standardized periapical radiographs and clinical photographs will be made.

Case report forms will be used to record the following observations for each implant site:

- Overall soft tissue health
- Plaque and gingivitis scores (modified Löe and Sillness)
- Pocket depth and clinical attachment level
- Implant Stability
- Retention and stability of prosthetic attachment
- Overall aesthetics (soft tissue contours)
- Assessment of reported pain
- Implant survival

Each participant will complete a patient satisfaction questionnaire. Participants will be asked to report their own assessments for the following criteria:

- Comfort
- Speech
- Appearance
- Ability to taste food
- Ability to chew food
- Pain on mastication
- General satisfaction

8.0 RADIOGRAPHIC AND PHOTOGRAPHIC SURVEYS

8.1 Cone Beam Computed Tomography

Cone beam computed tomography (CBCT) images will be used to obtain a 3-dimensional database of the patient's anatomy from the volumetric tomography. Axial, sagittal, and cross-images will be reconstructed to measure the tooth socket volume. Hounsfield units will be calculated to assess the relative tissue density for each study site. CBCT scans will be obtained after the completion of the extraction and grafting procedures and again at 8 weeks after the extractions.

8.2 Intra-oral radiographs

Standardized intra-oral periapical radiographs will be obtained of each site when the implants are placed and uncovered, at final implant restoration and at twelve and twenty-four months after the implants are placed. A minimum of five radiographs per study site over the duration of the study will be obtained. Additional radiographs may be obtained based on the study dentist's determination of need.

Radiographs will be used to monitor osseous health at the bone-implant interface, to verify implant position, to assess the quality of implant-attachment interface and to capture measurements of longitudinal osseous support to the implants.

8.3 Radiographic Image Acquisitions

Longitudinal measurement of osseous support to the implant sites is reliant upon serial radiographs of consistently similar quality that accurately image existing anatomy with minimal distortion over time. Ideal images for this study will center the targeted sites with at least 2mm of adjacent anatomy visible on each side of the implant.

Irregular projection geometry, variations in film positioning and mA/kVp of the X-ray beam and exposure time, coupled with poorly controlled film processing at the source (when film-based imagery is used) can influence image quality and thus can limit the accuracy of the analysis.

Taking radiographs from the same exact position at each designated interval reduces the possibility of geometric inaccuracy. Ensuring parallelism and standardization of periapical radiographs for measurement of osseous support is made possible by consistent use of a Rinn bite-block and aiming ring and careful positioning of film holding apparatus. This, coupled with fixed exposure time and standardized beam settings [milliamperage (mA) and kilovoltage (kVp)], will yield images with similar geometry and with constant density leading to a valid and dependable analysis.

8.4 Clinical Photography

Each study site will be monitored with digital photography to assess the soft tissue healing. Photographic assessment will be based on images taken at 1:1 ratio with a Nikon D-70 digital camera with a sunpack ringflash. Buccal and occlusal views will be obtained at the initial visit (prior to extraction), after completion of the grafting procedures, at 2 and 4 weeks, immediately prior to biopsy at 8-weeks, after implant insertion, at each prosthetic restorative visit, when the final restoration is attached and at four semi-annual follow-up visits.

9.0 ADVERSE EVENT REPORTING

9.1 Adverse Event Reporting

Participants will be interviewed at each visit and prompted to discuss any adverse events; such events will be recorded. In the event of a serious adverse event, the IRB will be notified per posted requirements and in full compliance with federal guidelines for research in human subjects. An event, whether study-related or not, will be assessed based on description of the event/pathology, onset, duration, severity, analgesics or other medication taken, and possible causality.

10.0 CRITERIA FOR SUCCESS

10.1 Grafts

The success criteria for this investigation are determined as follows: Grafts will be deemed successful if there are no reported symptoms or clinical signs or of post-application allergy, toxic reactions or evidence of gross local or systemic infections.

Histological and histomorphometric analyses will provide evidence of the relative success or failure of graft materials to enhance formation of new osseous tissue in extraction sockets. Results will be compared across experimental groups and between experimental groups and controls.

A site that fails to meet the stated criteria for success, or where the width of the ridge remains too narrow for implant insertion will be re-grafted (an offer that patients may decline). The site may receive an implant at a later date but the site will be exited from the study results.

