2.3 Hypotheses and Specific Aims

Hypothesis I

Bone grafted sites preserve alveolar ridge dimensions of extraction sockets more effectively than extraction sites that have healed without grafting.

Specific Aims

- 1: Compare alveolar ridge dimensions in grafted extraction sockets to that of sites healed without grafts after 8 weeks of post-extraction healing.

Hypothesis II

The addition of growth factors to bone grafting materials will enhance osseous and soft-tissue healing.

Specific Aims

- 2: Assess the efficacy of bone grafting with and without enrichment with growth factors to preserve the volume of bone in extraction sockets.

- 3: Compare soft tissue healing between groups at week-1, week-2, week-4 and after 8 weeks of post-extraction healing

- 4: Assess quantitative bone fill across groups after 2 months of post-extraction healing
- 5: Compare qualitative bone fill across groups after 2 months of post-extraction healing.
- 6: Assess and compare the relationship of osseous healing and implant stability at insertion across groups after 2 months of post-extraction healing.

Hypothesis III

Laser Thread Textured (LTT) dental implant will help preserve longitudinal peri-implant crestal bone more effectively than implants with Resorbable Blast Texturing (RBT).

Specific Aims

- 7: Assess the efficacy of LTT and RBT surface topographies when surgically implanted into extraction sockets.
- 8: Assess peri-implant soft-tissue healing adjacent to LTT and RBT surfaced implants.
- 9: Assess changes in longitudinal crestal bone level across extraction groups and between implant groups at 12 and 24 months after surgical implant placement.

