12.4 Statistical Analysis

The general approach to statistical analysis of the study aims will be based on mixed-model analysis of variance (ANOVA). This approach will accommodate the inclusion of correlated observations due to study subjects potentially contributing measurements of more than one single tooth site to the analysis.

The sample distributions will be examined for each outcome variable. If these distributions depart substantially from normality, transformations of the data will be evaluated. If normality cannot be established by transformation, rank-based analyses will be used.

Subjects will be included as a random effect on the analyses that include multiple observations per subject. For analysis of histological data, only one tooth site per subject will be evaluated and the model will not include a random effect.

Smoking status will be included in all models in order to account for differences in response between smokers and non-smokers, and so that the analysis will correspond to the study's randomization strategy. Comparisons between smokers and non-smokers are not a primary interest in the study.

For aims in which interaction terms are of interest, significant interaction terms will be investigated using plots of least square means and separate post-hoc analyses for individual time points.

Hypothesis 1

Differences among the four groups will be evaluated by the overall F-test for the ANOVA. Pairwise comparisons among group means will be conducted using Tukey's test. Contrasts will be constructed to address each specific aim (SA).

SA-1: Compare alveolar ridge dimensions in grafted extraction sockets to that of sites healed without grafts after 8 weeks of post-extraction healing.

This SA will be addressed by comparing the combined mean of the three graft groups (FDBA/TCP, DDBA/TCP/PRP, FDBA/TCP/PDGF) with that of the CONTROL group by calculating a contrast and the corresponding F-test. Pairwise comparisons among means will be conducted using Tukey's test..

Hypothesis II

The addition of growth factors to bone grafting materials will enhance osseous and soft tissue healing.

SA-2: Assess the efficacy of bone grafting with and without enrichment with growth factors to preserve the volume of bone in extraction sockets.

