This SA will be addressed using mixed-model ANOVA to compare mean bone volume among the four groups. Post-hoc pairwise comparisons will use Tukey's test. The effect of growth factors enrichment will be addressed using contrasts and F-tests to compare the mean of Group-4 with those of each of the other groups. If there is not a significant difference among the group means of Groups 1-3, the combined mean of these three groups will be compared with that of Group-4.

SA-3: Compare soft tissue healing between groups at week-1, week-2, week-4 and after 8 weeks of healing.

The analysis of SA-3 will be mixed-model ANOVA including measurements of healing made at each time points. Time will be included in the model in order to account for unequal spacing of the observational times. The statistical test that will be of primary interest will be the F-test for Group by time interaction.

SA-4: Assess quantitative bone fill across groups after 8 weeks post-extraction healing.

Qualitative bone fill will be compared among four groups using mixed-model ANOVA and the 8 week measurement only. Post-hoc pairwise comparisons will use Tukey's test.

SA-5: Compare qualitative bone fill across groups after 8 weeks post-extraction healing.

Percent new bone, percent residual graft, and percent soft-tissue will be compared among the four groups using ANOVA. For this analysis, there will be a single measurement of each of the variables per participant, so correlated observations will not be an issue in the analysis. Post-hoc pairwise comparisons will use Tukey's test.

SA-6: Assess the relationship of osseous healing and implant stability at insertion across groups after 8 weeks post-extraction healing.

This SA will be addressed by including the implant stability measure as a predictor variable in the analysis of osseous healing. The statistical test that will be of primary interest for this analysis will be the two-factor interaction of stability and group.

Hypothesis III

Laser thread-textured (LTT) dental implant will preserve longitudinal peri-implant crestal bone more effectively than implants with Resorbable blast texturing (RBT).

SA-7: Assess the efficacy of LTT and RBT surface topographies when surgically implanted into extraction sockets.

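### Section 10.1 calls a tolerability rule 'success' and exits narrow-ridge sites from the results, which read literally is an exclusion that depends on the SA-1 outcome

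*Combined protocol and SAP*

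**What the plan says.** Section 10.1 sets one categorical rule for grafts: "The success criteria for this investigation are determined as follows: Grafts will be deemed successful if there are no reported symptoms or clinical signs" of allergy, toxic reaction or gross infection. The next paragraph turns to bone, without a cut-off: "Histological and histomorphometric analyses will provide evidence of the relative success or failure of graft materials to enhance formation of new osseous tissue" in the sockets, compared across groups and with controls.

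The third paragraph gives two routes out: "A site that fails to meet the stated criteria for success, or where the width of the ridge remains too narrow for implant insertion". Such a site is offered re-grafting and may be implanted later, "but the site will be exited from the study results".

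Hypothesis I in section 2.3 concerns the ridge itself: "Bone grafted sites preserve alveolar ridge dimensions of extraction sockets more effectively than extraction sites that have healed without grafting". Section 12.4 tests it on ridge measurements. For SA-1: "This SA will be addressed by comparing the combined mean of the three graft groups" with that of the control group. For SA-2: "This SA will be addressed using mixed-model ANOVA to compare mean bone volume among the four groups". SA-4 compares bone fill and SA-5 the histological percentages. None of these, and no endpoint in section 12.3, takes graft success as an input. Section 12.4 names no analysis set and does not say how exited sites are handled.

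**The concern.** There are two problems, of unequal weight.

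The lesser one is the label. Section 10.1 lists a ridge too narrow for an implant as an alternative to failing the success criteria. A graft can therefore count as successful although its site cannot take an implant. Sites that fail the rule leave the results, so every graft still in the results has passed. The rule is also worded for grafts, and it is unclear whether it applies to the ungrafted control sites.

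The greater one is the second exit route. Whether a ridge is too narrow at week 8 is closely related to what SA-1 measures. If grafting works, more control than grafted sites should be too narrow. Removing them drops the worst outcomes, mostly from the control group, and pulls the contrast towards no difference. The randomised comparison for Hypothesis I would then be made on sites selected by their own result.

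**Working it through.** **Inputs.** From section 12.5: effective sample sizes of 25 control and 75 grafted sites for SA-1, a medium effect of 0.50 SD, two-sided testing at the 95% level, stated power about 57%, and about 0.65 SD detectable with 80% power. Also from 12.5: an effective total of 96, or 24 per group. Complication rates, exit rates and implantation rates are not in the documents and are assumed below.

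**1. The plan's own figure.** Standard error = √(1/25 + 1/75) = 0.231 SD. 0.50/0.231 = 2.165. Normal approximation: Φ(2.165 − 1.96) = 58.1%. The noncentral t-test gives 57.3%. At 0.65 SD the two methods give 80.4% and 79.6%. The stated 57% and 80% reproduce.

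**2. What the success rule reports.** If a fraction r of grafts has a listed complication, the pass rate is 1 − r whatever happened to the bone. For 60 grafted participants (3 × 20) with one site each, r = 2%, 5% and 10% gives 58.8, 57 and 54 passes. Once failing sites are exited, the rate among retained grafts is 100% by construction.

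**3. What the narrow-ridge exit does to SA-1.** Assume control sites are N(0, 1), grafted sites are N(0.50, 1), and every site below one common cut-off c is removed. With a fraction q of control sites exited, c = Φ⁻¹(q). For a group with mean μ, put a = c − μ and λ = φ(a)/[1 − Φ(a)]. Retained sites have mean μ + λ and variance 1 + aλ − λ².

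For q = 10%, c = −1.282:
- Control: λ = 0.195, variance 0.712, n = 22.5.
- Grafted: a = −1.782, exit rate 3.7%, λ = 0.085, mean 0.585, variance 0.842, n = 72.2.
- Difference = 0.585 − 0.195 = 0.390 SD.
- Standard error = √(0.712/22.5 + 0.842/72.2) = 0.208, and 0.390/0.208 = 1.873.
- Power = Φ(1.873 − 1.96) = 46.5%, or about 47%.

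| Control sites exited (assumed) | Grafted sites exited | Expected difference | Power |
|---|---|---|---|
| 0% | 0% | 0.50 SD | 58% |
| 5% | 1.6% | 0.43 SD | 52% |
| 10% | 3.7% | 0.39 SD | 47% |
| 20% | 9.0% | 0.33 SD | 38% |
| 30% | 15.3% | 0.28 SD | 30% |

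**4. How much a binary week-8 outcome could show.** Exact power of Fisher's test for 24 control v 72 grafted effective sites (3 × 24), at assumed proportions implanted: 70% v 95%, 85%; 80% v 95%, 53%; 85% v 95%, 32%; 90% v 95%, 13%.

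**The case against.** The best defence is that nothing depends on the label. Bone is tested on its own measures in SA-1, SA-2, SA-4 and SA-5, and the primary efficacy parameter in section 12.3 is implant survival. This stands. A reader might infer that every graft passes and that the trial cannot tell an effective graft from an inert one. The documents do not support that. Complications do fail a graft, passing is universal only among retained sites, and the bone analyses exist to separate the groups.

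A second defence is that section 10.1 itself assigns the relative success of the materials to histology. This also stands, but it gives no threshold, rests on one core per participant, and does not measure the ridge.

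Third, the exit clause sits in the sentence about a later implant and can be read as removing the site from the implant phase only. By section 5.1 the week-8 CBCT is made before the tissue is touched, so bone data can exist for exited sites. A reader might therefore go too far in saying that the week-8 result is certainly discarded. The text is ambiguous. But its words cover the study results as a whole, and section 12.4 contains nothing that narrows them.

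Finally, a binary implantation outcome coarsens what the plan measures on a scale. It also rests on a surgeon's judgement, and section 5.5 states blinding only for laboratory technicians. This is a fair reason to keep that outcome supportive.

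**Conclusion.** The point holds in a limited form. The success rule in section 10.1 is a tolerability rule, and a rate computed on retained sites would carry no information. This is a reporting fault, because no test uses the label. The more consequential fault is that the exit clause, read literally, removes sites according to the outcome SA-1 is meant to compare, and no analysis set corrects this.

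At an assumed 10% exit among controls, the expected difference falls from 0.50 to about 0.39 SD and power from about 58% to about 47%. Over assumed exits of 5% to 30%, power runs from 52% down to 30%. These figures assume a normal outcome, a true benefit of 0.50 SD, and one cut-off applied to the same quantity that SA-1 analyses. If the surgeon's decision tracks that quantity only loosely, the loss is smaller. If grafting has no effect, a common cut-off removes both groups equally and causes no bias. If only the implant phase was meant, a sentence saying so removes the problem.

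**What to change.** 1. In section 10.1, rename the present rule 'graft tolerability'.
2. For all randomised extraction sites in all four groups, controls included, report by arm the number exited under 10.1 and the reason.
3. Add a descriptive or supportive secondary outcome: the proportion of all randomised extraction sites implanted at week 8 without re-grafting, by arm, with exited sites counted as failures.
4. In section 12.4, state that exited sites stay in SA-1 and SA-2 using the week-8 CBCT, and that exit applies only to the implant-phase analyses. Name the CBCT as the source of the SA-1 ridge dimensions. Section 5.3 also records ridge measurements by probe once flaps are raised, and the plan does not say which set SA-1 uses.

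The cost is protocol and SAP wording, one more table, and reading the week-8 scans of exited sites. The week-8 decision is already made at each site. The limits are that the binary outcome rests on the surgeon's judgement, no blinding of surgeons is stated, and power is low for small differences (step 4 of the working). The clinical handling of such sites is not addressed here.

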4.2 Randomization

Participants will be stratified for smoking status and randomized to one of four extraction groups; three experimental groups utilizing three different bone grafting applications and a control group where extraction sockets will be allowed to heal naturally. A secondary randomization will be conducted to select one tooth site per subject to receive trephine sampling for histology evaluation. At the time of enrollment, each participant in groups 1-4 will be further randomized into one of two implant strata.

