4.7 Grafting Extraction Sockets

After extractions, sockets will be grafted according to each participant's assigned randomization group.

Group-1: Each socket will be irrigated with sterile saline and allowed to heal naturally [control group].

Group-2: Each socket will be grafted with freeze dried bone allograft (FDBA) mixed with Tri-calcium phosphate (TCP) 8:2 ratio; reconstituted with sterile saline.

4.7-2a Irrigate sockets with sterile saline

4.7-2b Pack the graft into each of the study sites using mild pressure achieving complete fill of the sockets.

4.7-2c Trim a 3mm section of collaplug and secure it over the grafted areas with 4.0 Vicryl crossing mattress sutures.

Group 3: Each socket will be grafted with an 8:2 ratio FDBA/TCP graft reconstituted with Platelet Rich Plasma (PRP).

4.7-3a Collect 9-18cc blood sample from the patient via venipuncture prepare the PRP following the Cascade Fibrinet System (Appendix A)

4.7-3b Mix PRP in the FDBA.TCP graft.

4.7-3c Irrigate sockets with sterile saline.

4.7-3d Pack the graft into each of the study sites using mild pressure achieving complete fill of the sockets

4.7-3e Trim a 3mm section of collaplug and secured it over the grafted areas with 4.0 Vicryl crossing mattress sutures.

4.7-3f Once secured in place, the soak the collaplug with PRP.

Group 4: Each socket will be grafted with an 8:2 ratio FDBA/TCP graft reconstituted with recombinant platelet derived growth factor (PDGF).

4.7-4a Irrigate sockets with sterile saline.

4.7-4b Apply PDGF into the sockets completely wetting all socket walls.

4.7-4c Mix PDGF with GEM-21S (product insert Appendix B)

4.7-4d Pack the graft into each of the study sites using mild pressure achieving complete fill of the sockets

4.7-4e Trim a 3mm section of collaplug and secure it over the grafted areas with 4.0 Vicryl crossing mattress sutures.

4.7-4f Once secured in place, soak the collaplug with PDGF.

After completion of procedures the Essix retainer (if used) will be fitted and placed.

A CBCT scan will be made to include images of each study site. Prescriptions for anti-bacterial mouth wash, antibiotics, and pain relief will be provided based on individual patient needs. An ice-pack will be dispensed. Verbal and written home care instructions will be given and the patient will be scheduled for a follow-up appointment.

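### Section 10.1 removes failed or too-narrow sites from the results without naming arms or aims; read literally, SA-1 loses randomised sites partly because of its own outcome

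*Combined protocol and SAP*

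**What the plan says.** Section 10.1 (Grafts) first defines graft success as freedom from allergy, toxic reaction and gross infection. It then says that a site failing those criteria, or one "where the width of the ridge remains too narrow for implant insertion will be re-grafted", leaves the study: "The site may receive an implant at a later date but the site will be exited from the study results". It gives no width threshold, names no arm or aim, and does not say what happens to data already collected.

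Section 4.2 randomises by participant: "Participants will be stratified for smoking status and randomized to one of four extraction groups". Table 2 places randomisation at the visit before extraction. The aim under Hypothesis I, SA-1 in section 2.3, is to "Compare alveolar ridge dimensions in grafted extraction sockets to that of sites healed without grafts after 8 weeks of post-extraction healing". Section 12.4 tests it by "comparing the combined mean of the three graft groups (FDBA/TCP, DDBA/TCP/PRP, FDBA/TCP/PDGF) with that of the CONTROL group".

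Two week-8 sources could supply ridge dimensions. Section 5.3 has a probe measurement taken at implant surgery after the flap is raised. Sections 4.9, 5.1 and 8.1 schedule a CBCT at 8 weeks, which section 5.1 places before any tissue is disturbed.

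Sections 12.3 to 12.5 define no analysis set, no handling of exited sites and no missing-data rule. The Manual of Procedures (Appendix E) is listed but was not available for this review.

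**The concern.** Ridge width is both a trigger for leaving the results and a component of what SA-1 measures. Removing such sites after randomisation selects the SA-1 data partly on the result. The direction of the error depends on a choice that the text leaves open:

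- **All arms.** The sentence speaks of a site without restriction. If grafting works, more control sites than grafted sites fall below the cut-off, the worst controls disappear, and the difference shrinks. With no true effect the arms are trimmed alike and type I error stays at about 5%.
- **Grafted sites only.** The section is headed Grafts and the remedy is to re-graft, whereas control sockets (section 4.7) receive no graft. Only the poorest grafted sites are then removed, so the comparison favours grafting even under the null.
- **Late-implant data only.** SA-1 is untouched.

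Because the readings pull in opposite directions, the choice should not be left open until data are available. SA-2 and SA-4 would lose the same sites, but are selected only as far as bone volume and bone fill correlate with width.

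**Working it through.** **1. The plan's own figure.** Section 12.5 gives effective sizes of 25 and 75, a difference of 0.50 sd, two-sided 5%, and about 57% power. The noncentrality is 0.50 / √(1/25 + 1/75) = 0.50 / 0.231 = 2.165. With 98 df the t test has 57.3% power, so the figure reproduces. At 0.65 sd, power is 79.6%, which matches the stated 80%.

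**2. Effect of trimming, independent sites.** Assumptions: width is normal with sd 1 and mean μ; sites below a common cut-off c leave; the analysed variable has sd 1 and correlation ρ with width. With a = c − μ and λ = φ(a) / (1 − Φ(a)), the kept sites have mean μ + ρλ and variance 1 + ρ²(aλ − λ²).

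Example: 10% of control sites exit, so c = −1.282; true effect 0.50 sd on both variables; ρ = 1.
- Control: λ = 0.195, mean 0.195, variance 0.712, 22.5 sites kept.
- Grafted: a = −1.782, λ = 0.085, mean 0.585, variance 0.842. Exits are 3.7%, so 72.2 sites are kept.
- All arms: difference 0.585 − 0.195 = 0.390; pooled sd √[(21.5 × 0.712 + 71.2 × 0.842) / 92.7] = 0.901; ratio 0.433; noncentrality 0.433 / √(1/22.5 + 1/72.2) = 1.79; power 42.6%.
- Grafted sites only, true effect zero, 10% of grafted sites exited: spurious benefit 0.195 − 0 = 0.195 sd. Simulated type I error is about 17%.

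**3. Clustered version.** Inputs from section 12.5: 80 participants, 120 sites, ICC 0.50. Section 12.4 adds a subject random effect: "Subjects will be included as a random effect on the analyses that include multiple observations per subject". Assumptions: half the participants have one site and half have two; ρ is the same at participant and site level; smoking is omitted. Simulation used 40,000 trials per cell with a REML random-intercept model, testing control against the mean of the three graft groups. With no exits, power is 54.6% and type I error 5.1%.

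| ρ with width | All arms, true 0.50 sd: power (%) at 2 / 5 / 10% of control sites exited | Grafted only, true zero: type I error (%) at 2 / 5 / 10% of grafted sites exited |
|---|---|---|
| 0.25 | 52.7 / 50.8 / 48.0 | 5.1 / 5.2 / 5.5 |
| 0.5 | 51.9 / 49.2 / 45.2 | 5.3 / 5.8 / 7.3 |
| 1 | 51.7 / 47.8 / 42.7 | 6.2 / 8.6 / 15.8 |

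Under the all-arms reading the apparent difference is 0.49 / 0.47 / 0.45 sd at ρ = 0.5 and 0.47 / 0.44 / 0.40 sd at ρ = 1. With no true effect, 10% exits and ρ = 1, it rejects 5.0% of the time. Under the graft-only reading the apparent benefit is 0.02 / 0.05 / 0.09 sd at ρ = 0.5 and 0.05 / 0.10 / 0.19 sd at ρ = 1.

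**4. Which ρ is plausible.** If SA-1 uses change between the two scans, with equal sd and scan-to-scan correlation k, the correlation of change with week-8 width is (1 − k) / √(2 − 2k). This gives 0.50, 0.39, 0.32 and 0.22 for k = 0.5, 0.7, 0.8 and 0.9. A cut-off that varies from site to site with sd s acts, under the graft-only reading, like ρ = 1 / √(1 + s²): 0.89, 0.71 and 0.50 for s = 0.5, 1 and 1.73. If week-8 width itself is analysed with a fixed cut-off, ρ = 1.

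The allergy, toxicity and infection triggers are not modelled.

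**The case against.** The strongest reply is that nothing orders the deletion of week-8 data. The sentence sets a later implant against exit from the results, so it can mean only that an off-schedule implant does not count. Section 12.4 defines SA-1 without invoking section 10.1, and the Manual of Procedures may settle the matter. This stands as a possible reading, which is why the point is conditional. It does not remove the problem: the words exit the site, not the implant, and nothing in the supplied text limits them.

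The reply is also right that the size is driven by assumption. No exit rate or correlation is documented, and the largest figures need a single cut-off. Section 5.4 lets the surgeon choose among diameters from 3.5 to 6.0 mm by tooth location, anatomy and bone volume, so a common cut-off is unlikely.

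A reader might infer the all-arms reading from the sentence "Results will be compared across experimental groups and between experimental groups and controls". It follows, and refers to, the histological and histomorphometric analyses. It does not say that the exit rule covers controls; the all-arms reading rests on the unrestricted wording alone.

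Two practical objections also stand. Keeping exited sites by wording alone cannot secure SA-5, because section 5.5 takes the core with the trephine that starts the implant osteotomy. Nor does it supply a usable week-8 value for a site re-grafted before week 8. The fix deals with both.

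**Conclusion.** The point holds as a conditional one. Section 10.1 states an exit rule whose literal application removes randomised sites from SA-1 partly on ridge width, and the supplied analysis sections do not undo it.

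The size rests on assumed exit rates of 2–10%. At 2–5% exits and a correlation of 0.5 or less it is small. It becomes material near 10% exits or if width itself is analysed. The type I error of about 16% is an upper case: it needs the graft-only reading, 10% exits, width as the outcome and one cut-off for all sites.

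A reader might go further and conclude that the trial is biased in favour of grafting, or that week-8 data will certainly be discarded. The documents support neither. The all-arms reading works against grafting, the late-implant reading leaves SA-1 intact, and the text does not choose. It should be fixed because SA-1 has only 57% planned power for a medium effect and the remedy is nearly free. Confidence is medium.

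**What to change.** - **Section 10.1, last sentence.** State that exited sites in every arm, control included, stay in the participant's randomised group for SA-1, SA-2, SA-3 and SA-4, using all data collected before any re-grafting, including the scheduled week-8 CBCT. They leave only the analyses that need a study implant (SA-6 to SA-9).
- **SA-5.** Keep the site when a core was obtained; otherwise report it as missing, by arm.
- **Section 12.4.** Base SA-1 on the week-8 CBCT, which does not depend on implant surgery, rather than only on the probe reading.
- **Sites re-grafted before week 8.** Treat the week-8 value as missing, keep the participant's other sites and earlier data in the mixed model, and add a sensitivity analysis that assigns such sites an unfavourable value.
- **Reporting.** Give exits by arm and by reason.

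The clinical decision to re-graft is unchanged. The cost is protocol and SAP wording and slightly more analysis work; no visit, scan or procedure is added.
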